Breathalyser tests will be used at each visit for the following reasons:

- Screening & re-screening – To assess eligibility
- Baseline visit (1st infusion) – To assess eligibility/ensure safety of IMP administration/ensure patient is able to complete cognitive tasks and questionnaires, as well as engage with therapy/education
- Visit 3, 5, 7 & 8 – To ensure patient is able to complete cognitive tasks and questionnaires, as well as engage with therapy/education
- Visit 4 & 6 (2nd & 3rd infusion) – To ensure safety of IMP administration/ensure patient is able to complete cognitive tasks and questionnaires, as well as engage with therapy/education
- Visit 9 & 10 - To ensure patient is able to complete cognitive tasks and questionnaires

Once randomised, if a patient attends for any visit and does not blow 0 on the breathalyser the visit will be terminated (either for the primary purpose of safety on infusion visits or of data integrity on non-infusion visits) and the patient invited to re-attend to complete the visit within the allocated visit window.

Concomitant Medication: All prescription medication, over-the-counter medication, vitamins, and/or herbal supplements will be recorded on case report forms (CRFs).

Vital Signs: Resting pulse, pulse oximetry and blood pressure (BP) measurements will be measured at each visit phase for safety monitoring. Vital signs will be continuously monitored throughout the infusion until the participant has recovered. This monitoring will be recorded on a standard

observation chart, stored as source data. The eCRF will record 3 sets of readings, one prior to the infusion, another after the infusion terminates, and then finally after the participants recovery.

Physical Examination: Height, weight and oral/tympanic temperature will be recorded.

At screening a physician will perform a physical examination of the cardiovascular, respiratory, GI and neurological system to a level of detail that would be expected for a patient due to receive anaesthesia.

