### **9.12 Assessment of compliance**

Compliance includes both adherences to IMP and Protocol study procedures. The trial medication will be administered by the research anaesthetist only in the context of the patient attending the Clinical Research Facility. Patients will not be responsible for any trial medication. A member of the research team will ensure that the arrangements for each treatment visit are agreed with the participant and their carer. Where necessary, the researcher will assist in transportation. If a participant fails to attend a clinic visit for the infusion then the researcher will endeavour to contact the patient to identify the reason. Where possible an alternate appointment will be made within the infusion visit window (see Appendix B). If the participant fails to attend a clinic visit for the follow-up day the researcher will endeavour to contact the patient to identify the reason and where possible arrange an alternative visit within the follow up visit window (see Appendix B). All episodes of failure to attend will be recorded in the medical notes, CRF and protocol deviation log. If the participant misses 2 consecutive infusions, then they will be withdrawn from treatment and will be invited to attend follow up visits 9 and 10 as part of our intention to treat protocol. Noncompliance to the Protocol study procedures will be documented by the investigator and reported to the Sponsor as agreed. Persistent noncompliance (<80%) may lead the patient to be withdrawn from the study.

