### **13.3.2 Primary outcome analysis**

There are two primary outcomes: (i) proportion relapsed (recommenced using alcohol) at 6-month follow-up; and (ii) percentage of days abstinent at 6-month follow-up (the denominator being 175 days). The proportion of relapsed participants at 6-month follow-up will be reported as a percentage for each arm, as well as for the ketamine arms combined and

the psychotherapy arms combined. Although no formal power calculations for a between-group analysis have been performed, the proportion of relapsed participants at 6-month follow-up will be expressed as a relative risk (RR) with a 95% confidence interval for the following comparisons: (i) all ketamine participants versus all non-ketamine participants; (ii) ketamine + psychotherapy participants versus ketamine + non-psychotherapy participants; and (iii) ketamine + psychotherapy participants vs. placebo + no psychotherapy participants. These analyses are purely exploratory and should be viewed with caution both in the light of lack of power and multiple testing. Percentage of days abstinent at 6-month follow-up will be reported descriptively in the same way by arm and combination of arms; additionally, the between-group mean differences and 95% confidence intervals will be reported for the comparisons set out above; again, these analyses should be regarded as exploratory. The primary analysis will be an intention-to-treat (ITT) complete case analysis including all randomised participants. A secondary analysis will be conducted including only those participants deemed to have completed to a sufficient degree their allocated interventions, that is, a per protocol analysis. All analyses will be performed by a statistician who is blinded to the treatment allocations and will be performed using Stata v.13.

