4.4 Study design

KARE has two interventions (drug therapy and psychological therapy), each with two possible forms, resulting in a two by two factorial intervention design, with a total of four possible interventions (Section 4.1).

The drug intervention will be administered by the site anaesthetist, who will be blinded to drug allocation and psychotherapy allocation. Psychotherapy/psychoeducation will be administered by the trial psychologists at each site who will be blinded to the drug allocation. Participants will also be blinded to drug allocation. Participant outcome data will be collected by site investigators who are blinded to drug allocation. The trial statistician will be blinded to both drug allocation and psychotherapy allocation throughout the trial.

Participants will be randomised to the trial after eligibility has been confirmed via prescreening and screening, and after having provided informed consent. The SCRAM-X ankle monitor (measuring alcohol levels in sweat) will be attached at screening. Treatment will commence as soon as possible after randomisation, and continue for a period of 3 weeks (one infusion session and two sessions of psychological therapy/psychoeducation per week). Follow-up data will be collected at 3 and 6 months after baseline. The last follow-up visit is scheduled for 24 weeks post baseline.

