4.5 Purpose of the analyses

The purposes of the analyses are as follows:

- (i) to provide baseline descriptive data by trial arm;
- (ii) to assess the feasibility of data collection;
- (iii) to assess loss to follow-up at 3 and 6 months;

- (iv) to assess the proportion of missing data at 6 months;
- (v) to provide descriptive outcome data by trial arm (ketamine vs placebo, psychotherapy vs psychoeducation, and all four arms individually) at 6 months;
- (vi) to provide relative risks (with 95% confidence intervals) for relapse of alcohol consumption comparing (a) ketamine vs placebo; (b) ketamine plus psychotherapy vs ketamine plus psychoeducation; (c) ketamine plus psychotherapy vs placebo plus psychoeducation;
- (vii) to provide mean difference (with 95% confidence intervals) for percentage of days abstinent at 6-month follow-up for the same combinations by arm as for (vi); and
- (viii) to descriptively report adverse events.

All inferential analyses are to be regarded as exploratory and viewed with caution due to lack of statistical power and multiple testing. For the primary outcomes, the primary analyses will be performed on an intention to treat (ITT) basis using complete case data only (see Section 6.5 for approaches to missing primary outcome data). As a sensitivity analysis, the inferential analyses for the primary outcomes only (vi and vii above) will be performed using only those participants deemed to have completed their allocated interventions to a specified degree (per protocol analysis). For the participants who receive ketamine, a per protocol treatment will be defined as receiving three or more infusions. No specification of a minimum treatment has been defined for psychotherapy/psychoeducation. Hence, all participants who receive placebo drug therapy will be considered as having been treated per protocol. For the secondary outcomes, only an ITT analysis using complete case data will be performed. All analyses will be performed by a statistician who is blinded to treatment allocation. All analyses will be performed using Stata v14.

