Table 5 Relapse of alcohol use and percentage of days abstinent at 6-month follow-up: per protocol^a population using complete case data.

Outcome	Ketamine (n=)	Placebo (n=)	PT (n=)	PE (n=)	Ketamine + PT (n)	Ketamine + PE (n)	Placebo + PT (n)	Placebo + PE (n)	Ketamine vs placebo RR (95% CI)	Ketamine + PT vs Ketamine + PE RR (95% CI)	Ketamine + PT vs placebo +PE RR (95% CI)
Relapse; n (%) Timeline follow back											
									Ketamine vs placebo mean difference (95% CI)	Ketamine + PT vs Ketamine + PE mean difference (95% CI)	Ketamine + PT vs placebo +PE mean difference (95% CI)
Percentage days abstinent; mean (SD); median [IQR] Timeline follow back											

^aPer protocol population defined as receiving at least three ketamine infusions. No definition of per protocol for placebo, psychotherapy, or psychoeducation interventions.

PE: Psychoeducation

PT: Psychotherapy

Table 6 Relapse of alcohol use and percentage of days abstinent at 6-month follow-up: intention to treat population using complete case and imputed data.

Outcome	Ketamine (n=)	Placebo (n=)	PT (n=)	PE (n=)	Ketamine + PT (n)	Ketamine + PE (n)	Placebo + PT (n)	Placebo + PE (n)	Ketamine vs placebo RR (95% CI)	Ketamine + PT vs Ketamine + PE RR (95% CI)	Ketamine + PT vs placebo +PE RR (95% CI)
Relapse; n (%) Timeline follow back											
									Ketamine vs placebo mean difference (95% CI)	Ketamine + PT vs Ketamine + PE mean difference (95% CI)	Ketamine + PT vs placebo +PE mean difference (95% CI)
Percentage days abstinent; mean (SD); median [IQR] Timeline follow back											

PE: Psychoeducation

PT: Psychotherapy

Table 7 Secondary outcomes at 3-month follow-up

Outcome	Ketamine (n=)	Placebo (n=)	PT (n=)	PE (n=)	Ketamine + PT (n)	Ketamine + PE (n)	Placebo + PT (n)	Placebo + PE (n)	Ketamine vs placebo mean difference (95% CI)
Number of continuous days abstinent ^{a,b} ; mean (SD), median [IQR]									
Percentage days abstinent ^{a,b} ; mean (SD); median [IQR]									

PE: Psychoeducation

PT: Psychotherapy

^aAbstinent means not using alcohol at all.

^bOutcomes measured using timeline follow-back.

Table 8 Secondary outcomes at 6-month follow-up

Outcome	Ketamine (n=)	Placebo (n=)	PT (n=)	PE (n=)	Ketamine + PT (n)	Ketamine + PE (n)	Placebo + PT (n)	Placebo + PE (n)	Ketamine vs placebo mean difference (95% CI)
Profile of Mood states; mean (SD), n									
Beck Depression Inventory; mean (SD)									
Hamilton Depression Scale; mean (SD), n									

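### The SAP applies the three-infusion per-protocol minimum to ketamine participants only, which can bias two of the three per-protocol comparisons

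*SAP*

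**What the plan says.** SAP 4.5 sets the per-protocol population used to re-run the inferential analyses of the two primary outcomes. For one drug arm: "For the participants who receive ketamine, a per protocol treatment will be defined as receiving three or more infusions". Three is the full planned course (SAP 4.1), so one missed infusion excludes the participant. For the other arm: "all participants who receive placebo drug therapy will be considered as having been treated per protocol". The SAP presents the placebo rule as following from the absence of any minimum for psychotherapy or psychoeducation. The footnote to the Table 5 shell in the SAP appendix repeats it: "No definition of per protocol for placebo, psychotherapy, or psychoeducation interventions".

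Protocol 13.3.2 describes the same analysis without any difference between arms: "A secondary analysis will be conducted including only those participants deemed to have completed to a sufficient degree their allocated interventions". Protocol 8.1 and SAP 4.1 give both drug arms three infusions.

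**The concern.** The SAP's reasoning does not support its rule. Having no minimum for the psychological intervention says nothing about the number of placebo infusions, which can be counted exactly as ketamine infusions can. A placebo participant who stopped after one infusion stays in the set; a ketamine participant with the same history is removed.

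That matters if participants who miss infusions differ in relapse risk. One route is in Protocol 7.9.1: after randomisation, "if a patient attends for any visit and does not blow 0 on the breathalyser the visit will be terminated". The participant may come back within the visit window, but someone who keeps drinking and does not complete the visit in time loses that infusion. Protocol 9.12 adds: "If the participant misses 2 consecutive infusions, then they will be withdrawn from treatment". Such participants are still invited to visits 9 and 10 (Protocol 7.11.1 and 9.12), so they can have a 6-month outcome and enter the complete-case data. These procedures are the same in both drug arms; only the exclusion differs.

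Table 5 is the planned check on the ITT result for both primary outcomes. If it favours ketamine because of how the set is built, its agreement with ITT would be no reassurance.

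**Working it through.** **The plan's own figures.** The documents give no number for this rule and no rate of incomplete infusions. The nearest figure is the precision statement in SAP 4.6, a 95% CI about 37 points wide for 25% relapse in the ketamine arm. The exact interval for 6/24 is 9.8% to 46.7%, width 36.9 points, so it reproduces. It confirms that the planning case is 24 per drug arm after 50% drop-out.

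**Inputs.**
- Overall relapse p: 50% (SAP 4.6), and 70% at 6 months as an alternative (Protocol 2.1).
- f, the share with a 6-month outcome but fewer than three infusions: assumed 10% or 25%.
- q, relapse in that share: assumed 75% to 100%.
- No drug effect, and the same f and q in both arms, so the true RR is 1.00.

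**Formula.** Per-protocol relapse on ketamine = (p − f·q)/(1 − f). On placebo it stays at p, because nobody is removed. RR is the ratio of the two.

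Example: p = 0.50, f = 0.25, q = 0.75 gives (0.50 − 0.1875)/0.75 = 0.417, and 0.417/0.50 = 0.83.

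**Results.** The false-favour columns give the share of 200,000 simulated trials, 24 per drug arm, in which the 95% CI for the RR (log scale, unadjusted for site) lies wholly below 1.

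| p | f | q | Ketamine per-protocol relapse | RR | False favour, SAP rule | False favour, same rule in both arms |
|---|---|---|---|---|---|---|
| 50% | 10% | 80% | 46.7% | 0.93 | 3% | 2% |
| 50% | 10% | 100% | 44.4% | 0.89 | 4% | 2% |
| 50% | 25% | 75% | 41.7% | 0.83 | 5% | 2% |
| 50% | 25% | 100% | 33.3% | 0.67 | 12% | 1% |
| 70% | 10% | 80% | 68.9% | 0.98 | 2% | 2% |
| 70% | 10% | 100% | 66.7% | 0.95 | 3% | 2% |
| 70% | 25% | 75% | 68.3% | 0.98 | 2% | 2% |
| 70% | 25% | 100% | 60.0% | 0.86 | 6% | 2% |

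With the same rule in both arms the expected RR is 1.00 in every row.

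**Direction.** If q = p there is no shift: at p = 0.50, f = 0.20, (0.50 − 0.10)/0.80 = 0.50. If non-completers relapse less, it reverses: with q = 0.30, (0.50 − 0.06)/0.80 = 0.55, RR 1.10.

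**Days abstinent.** If non-completers have d points fewer days abstinent than completers, removing them from ketamine alone adds f·d points in ketamine's favour: 0.10 × 20 = 2 up to 0.25 × 40 = 10 points (d assumed).

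**Comparisons affected.** Ketamine versus placebo, and ketamine plus psychotherapy versus placebo plus psychoeducation. Ketamine plus psychotherapy versus ketamine plus psychoeducation has the same rule on both sides.

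**The case against.** The strongest reply is that little hangs on this analysis. It is a labelled sensitivity analysis, all inference is declared exploratory (SAP 4.5), no p-values are reported (SAP 6.4), the footnote discloses the rule, and ITT is primary and untouched. All of that stands and limits the consequence. It does not make the rule right: a sensitivity analysis with a built-in imbalance is a poor check.

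The link to drinking is also looser than it first appears. A positive breath test ends that visit, but the second and third infusions have windows of 4 to 21 days after the previous one, so re-attendance can rescue the infusion. Drinking below the relapse threshold is only a lapse (Protocol 4.1). The two-missed-infusions rule adds no new exclusions, since anyone it catches already has fewer than three. Side-effect withdrawal (Protocol 9.11) is the cause most specific to ketamine and need not go with more relapse. This is why f and q are shown as a range and the direction is left open.

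Three stronger readings are tempting and not supported:

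- **That the rule breaks the analyst's blind.** SAP 4.4 says "The trial statistician will be blinded to both drug allocation and psychotherapy allocation throughout the trial", and a ketamine-only exclusion does require knowing who had ketamine. But the planned ITT contrasts already reveal it: one comparison is within ketamine, so whoever runs the three contrasts can tell the drug arms apart. The statistician also receives the allocation codes to prepare envelopes (SAP 4.3, Protocol 7.2). One rule for both arms would not restore blinding.
- **That the rule would greatly inflate the planned effect.** From 12/48 versus 24/48 (RR 0.50), removing five ketamine participants, four or five of them relapsed, gives (8/43)/(24/48) = 0.37 or (7/43)/(24/48) = 0.33. Removing the same from both arms gives (8/43)/(20/43) = 0.40 or (7/43)/(19/43) = 0.37. About three quarters of the shift comes from restricting to completers at all, not from the asymmetry.
- **That false favour would reach nearly 30%.** At 50% relapse and 48 per drug arm with no loss to follow-up, the same four scenarios give about 4% to 29%. Both documents plan on 24 per drug arm, and the top figure needs a quarter of participants to be incomplete, followed to 6 months, and all relapsed.

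**Conclusion.** Wrong as written. The rule treats two three-infusion arms differently, the reason given does not justify it, and it departs from Protocol 13.3.2. It can bias two of the three per-protocol comparisons on both primary outcomes.

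The likely size is modest: under the assumed scenarios an expected RR of 0.93 to 0.67 at 50% relapse, or 0.98 to 0.86 at 70%, where the truth is 1.00. These figures rest on assumed f and q, equal non-completion in the two arms, and no site adjustment. A reader might infer that the rule must favour ketamine. The documents do not establish that: it favours ketamine only if participants short of three infusions relapse more than average. The ITT results and the within-ketamine comparison are not affected.

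**What to change.** In SAP 4.5, replace the ketamine-only definition and the sentence on placebo with one rule: in both drug arms, per protocol means having received all three allocated infusions, ketamine or placebo; no minimum is set for psychotherapy or psychoeducation. Change the Table 5 footnote to match, and report in Table 5 the number excluded per arm by reason (for example positive breath test, side effect, missed visit, other).

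The cost is a few sentences and a footnote. Study drug treatment is already recorded in the CRF for every participant (Protocol 11.2). The downside is a smaller placebo per-protocol set with slightly wider intervals. The set will still not be a randomised comparison, because side-effect withdrawals will fall mainly on ketamine, so ITT should remain primary and the exclusion counts should be read beside the estimate.

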4.6 Sample size calculation

As this is a proof of concept study, no inferential analyses are planned, therefore no formal power calculations have been performed. The sample size of 96 (24 participants per treatment combination) was selected for the following reasons. As a proof of concept study, feasibility of recruitment, and desire to minimise the number of subjects, were considerations. If a level of dropout of 50% is observed, this will leave 12 participants per arm, 24 receiving ketamine and 24 receiving placebo. We anticipate a relapse rate of 50% in the placebo arm, and would be able to estimate a reduced relapse rate of 25% in the ketamine arm with a 95% CI width of 37 percentage points (see Protocol Final Version 12, 20.01.2020 Section 13.2.1 for further details).

4.7 Study populations

Inclusion and exclusion criteria for participants are set out in the Protocol, Final Version 12, 20.01.2020 Section 5.

The primary analyses will be performed using the ITT population (participants analysed according to their randomised allocations). Further sensitivity analyses will be performed using the per protocol population (defined in Section 4.5). All analyses will be performed using complete case data only. Participants found to be ineligible after randomisation will be excluded from all analyses.

5. Study objectives and endpoints

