### **7.11.1 Discontinuation from treatment**

The investigator may discontinue a patient from treatment if it is considered necessary for any reason including:

- Ineligibility (either arising during the study or retrospective)
- Significant protocol deviation e.g. if treatment is stopped for longer than 21 days (All protocol deviations and violations will be recorded and reported to the sponsor)
- Significant non-compliance with treatment or study requirements e.g. If the participant misses 2 consecutive infusions, as detailed in section 9.12
- An adverse event which requires discontinuation of the study medication or results in inability to continue to comply with study procedures
- Disease progression which requires discontinuation of the study medication
- Pregnancy
- In the case of an overdose (see section 10.5.5)

Where treatment is discontinued, participants will be invited to attend follow up visits 9 & 10 on the basis of our planned intention to treat analysis which assumes (and formally tests: see section 13.3.4) that data are missing at random.

The reason for participant treatment discontinuation will be recorded in the case report form (CRF).

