5.1 Study objectives

The objectives of the study are as follows (Protocol, Final Version 12, 20.01.2020 Section 3).

Primary objectives

- 1) To obtain preliminary data on whether ketamine is effective in promoting and prolonging abstinence in alcohol dependent patients following detoxification.
- 2) To assess safety and tolerability of ketamine in alcohol dependence.

Secondary objectives

- 1) To make an early assessment on likely compliance to a combined ketamine and relapse prevention based cognitive behavioural therapy (CBT).
- 2) To obtain preliminary data as to whether ketamine alone is as effective as a combined ketamine and psychotherapy treatment.

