6.5 Missing data

The primary analyses for primary and secondary outcomes will be based on complete case data only. For the primary outcomes only, we will use multiple imputation to impute any missing data, if data are missing for more than 5% of participants. Individual item missingness for questionnaire outcomes will be dealt with by using the average of reported items to substitute for missing items if no more than a certain number (to be determined for each questionnaire) of items are missing.

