6.6 Adverse events

Data on adverse events will be set out descriptively by trial arm.

7 Audit trail

Date of SAP	SAP version number	Date presented to Trial management group/Trial steering committee	Significant amendments since previous version	Date approved
15 June 2016	1.0	15 June 2016	N/A	15 June 2016
2 December 2019	1.1	5 December 2019	1. Inferential analyses to be adjusted by site (Section 7.3)	5 December 2019
27 January	1.1 (supersedes v1.1. 2/12/2019)	27 January 2020	1. Definition of primary outcome refined and data source for primary outcome confirmed (Section 5.2). 2. Protocol version amended in anticipation of submission (Version 12, 20.01.2020)	27 January 2020
11 March 2020	1.2	12 March 2020	1. Confirmation of use of Protocol Final Version 12, 20.01.2020 (throughout).	12 March 2020

8 References

1. *International Conference on Harmonisation of Technical Requirements for Registration of Pharmaceuticals for Human Use. Statistical Principles for Clinical Trials. Guideline E9.* http://www.ich.org/fileadmin/Public_Web_Site/ICH_Products/Guidelines/Efficacy/E9/Step4/E9_Guideline.pdf (last accessed 25 April 2016)

9 Appendix – example figures and tables

Figure 1 Participant flow diagram

[figure not shown]

Table 3 Participant characteristics at baseline

Participant characteristic	Ketamine + psychotherapy (N=)	Ketamine + psychoeducation (N=)	Placebo + psychotherapy (N=)	Placebo + psychoeducation (N=)
Gender; n (%)				
Male				
Female				
Age; mean (SD); [min, max]				

Table 4 Relapse of alcohol use and percentage of days abstinent at 6-month follow-up: intention to treat population using complete case data.

Outcome	Ketamine (n=)	Placebo (n=)	PT (n=)	PE (n=)	Ketamine + PT (n)	Ketamine + PE (n)	Placebo + PT (n)	Placebo + PE (n)	Ketamine vs placebo RR (95% CI)	Ketamine + PT vs Ketamine + PE RR (95% CI)	Ketamine + PT vs placebo +PE RR (95% CI)
Relapse; n (%) Timeline follow-back											
									Ketamine vs placebo mean difference (95% CI)	Ketamine + PT vs Ketamine + PE mean difference (95% CI)	Ketamine + PT vs placebo +PE mean difference (95% CI)
Percentage days abstinent; mean (SD); median [IQR] Timeline follow-back											

PE: Psychoeducation

PT: Psychotherapy

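### SAP 4.7 drops participants found ineligible after randomisation from every analysis, adverse events included, and no safety population is defined

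*SAP*

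**What the plan says.** SAP 5.1 repeats the protocol's second primary objective: "To assess safety and tolerability of ketamine in alcohol dependence". SAP 4.5 sets out eight purposes of the analyses, the eighth being "to descriptively report adverse events".

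SAP 4.7 names two populations, intention to treat (by allocation) and per protocol. It then gives two rules without exceptions:

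- "All analyses will be performed using complete case data only"
- "Participants found to be ineligible after randomisation will be excluded from all analyses"

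SAP 6.6 is one sentence: "Data on adverse events will be set out descriptively by trial arm". It names no population and no denominator. The SAP appendix has no shell for an adverse-event table. The nearest item is a row in Table 8 for the adverse effects visual analogue scale, which is a 6-month secondary outcome. Protocol 13.3 has no safety analysis section, and protocol 13.5 says only that the trial team monitors adverse events.

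On missing data, SAP 6.5 says: "The primary analyses for primary and secondary outcomes will be based on complete case data only". It then provides for multiple imputation of the primary outcomes.

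Protocol 7.11.1 gives, as one ground for stopping treatment, "Ineligibility (either arising during the study or retrospective" (the bracket closes there). Protocol 7.11.2 repeats this ground for withdrawal from the trial. Protocol 7.9.2 has eligibility reviewed when a laboratory result is abnormal and clinically significant.

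**The concern.** A safety table should count everyone exposed to the drug. Whether a participant should have been enrolled has no bearing on whether an infusion harmed them. A person enrolled in error and then infused is, if anything, a case that a safety report should show.

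The SAP supplies no exposed population and gives an explicit instruction to remove one group of potentially exposed people. With 48 participants planned per drug arm and purely descriptive reporting, one or two missing events can change what the table conveys on a primary objective.

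There is a further possibility. Several exclusion criteria in protocol 5.2 are also conceivable harms: liver tests above three times normal, seizure, psychosis, suicidal ideation and allergic reaction to ketamine. If one of these arose after dosing and was classed as ineligibility, the event itself would trigger its removal from the table.

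**Working it through.** **1. Does the ineligibility rule reach adverse events?**

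- SAP 4.5 counts adverse-event reporting as one of the analyses.
- SAP 4.7 removes participants found ineligible from all analyses.
- SAP 6.6 restores nobody.
- No passage in the SAP or protocol defines a safety set that would override 4.7.

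So the rule reaches adverse events. It also sits badly with protocol 7.2 and 13.3.2, which keep all randomised participants in the intention-to-treat analysis.

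**2. Size of the ineligibility effect.** Planned ketamine participants: 24 per combination × 2 = 48 (protocol 13.2.1, SAP 4.6). Assume all 48 start at least one infusion.

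- One event, in a participant later found ineligible: true 1/48 = 2.1%; tabulated 0/47 = 0%.
- One-sided 95% upper bound for zero events, 1 − 0.05^(1/n): n = 48 gives 6.1%; n = 47 gives 6.2%.
- If instead the excluded person had no event and someone else did: 1/48 = 2.1% becomes 1/47 = 2.1%.

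The denominator hardly moves, so a reader would get no warning from it. The damage arises only when the excluded person is one who had the event.

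**3. Does the complete-case rule reach adverse events?** Taken literally, yes. But the same literal reading would also cover purposes (iii) and (iv) in SAP 4.5 (loss to follow-up and proportion missing), which cannot be done on complete cases. It would also forbid the imputation in SAP 6.5 and Table 6. SAP 4.5, 6.2 and 6.5 each attach complete case to primary or secondary outcomes. A complete case is never defined for event counts, and adverse events are reviewed at every visit from 2 to 10 (Appendix B), so events before loss are recorded. The rule clearly applies to the adverse effects visual analogue scale, because that is a listed secondary outcome.

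**4. Worst case if it did.** The plan's own retained number reproduces: 96 × (1 − 0.50) / 2 = 24 per drug arm. Zero-event upper bound and chance of seeing at least one case of an event with a true rate of 5%, 1 − 0.95^n:

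| Dropout | n | Upper bound | Chance of at least one |
|---|---|---|---|
| 0% | 48 | 6.1% | 91.5% |
| 25% | 36 | 8.0% | 84.2% |
| 50% | 24 | 11.7% | 70.8% |

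The 25% row is an assumed intermediate value. The chance column assumes that loss is unrelated to harm.

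**The case against.** The strongest reply is that a competent analyst would never build an adverse-event table this way. Being found ineligible most naturally means discovering later that entry criteria were not met. Protocol 7.11.1 governs stopping treatment rather than analysis, and it has a separate ground for adverse events. Appendix B schedules eligibility determination only up to baseline. Serious events are recorded and sent to the sponsor separately under protocol 10.4, and the study is a descriptive proof of concept.

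Much of this stands. No passage says that a new psychosis or raised liver tests after dosing would be reclassified as ineligibility; that route is open under protocol 7.11.1, 7.11.2 and 7.9.2 but is inference. The reply does not rescue the rule, however. Even if ineligibility is only ever retrospective, the person was infused and their events still leave the table. Sponsor reporting of serious events does not correct the trial's own by-arm table.

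A reader might also infer that everyone lost to follow-up disappears from adverse-event reporting, halving the ketamine denominator. The documents do not support that, for the reasons in step 3 of the working. In addition, the 50% is described in protocol 13.2.1 as a very conservative allowance, and the infusions take place early, at visits 2, 4 and 6.

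**Conclusion.** The point holds for the ineligibility rule. SAP 4.7 contains a wrong instruction for safety reporting, not just a missing detail, and no safety population exists to override it. How many participants it would affect cannot be known from the documents; the illustration of 1/48 shown as 0/47 assumes that all 48 are dosed and that the excluded participant had the only event.

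The complete-case sentence is loosely worded and should be confined, but the fall from 48 to 24 is a worst-case bound, not a prediction.

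A reader might go further and conclude that adverse-event rates will be biased downward, mainly in the ketamine arms. The documents do not show this. They give no reasons for loss or ineligibility by arm, and dropout could equally follow relapse in either arm. Attrition is to be reported by arm (protocol 13.3.3), so lost participants remain visible.

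**What to change.** Before the adverse-event table is produced:

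- In SAP 4.7, limit both the complete-case rule and the ineligibility exclusion to efficacy and other outcome analyses.
- In SAP 4.7 and 6.6, define a safety set: every participant in whom at least one infusion was started, grouped by drug received, regardless of later eligibility, withdrawal or availability of 6-month data.
- Show the safety-set denominator in the adverse-event table.
- State in the table that it covers events recorded in the CRF. Protocol 10.2 and 11.2 keep expected non-serious events in source documents only, so the trial database cannot supply them.

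The cost is a few sentences in the SAP and a table footnote. No extra data collection, no change to the sample size and no change to any clinical rule is needed.
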